4.3. Analysis populations

The VITAL trial asses a model of HIV care in a "real-world" setting. The main interest is to assess effectiveness of the VITAL intervention, i.e. the degree of effect under "real-world" conditions. Accordingly, the ITT population is the analysis population of most relevance. Therefore, in the primary analysis, we will analyse participant outcomes in the cluster they were enrolled in, independent of their follow-up. As a sensitivity analysis we will conduct a per-protocol analysis

includes participants for whom the VITAL intervention was technically successful defined as all viral loads available in the VITALapp \leq 31 days after phlebotomy.

5. Trial population

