5.4. Withdrawal/follow-up

The CONSORT flowchart will summarize disengagement from care as well as reason for it (dead, hospitalized, transfer-out, stopped ART no information found after tracing) and study withdrawal, by group.

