6.2. Analysis methods

General: Continuous variables will be inspected using histograms: 1) to assess for outliers which may be queried for accuracy, and 2) to assess whether appropriate transformations are required for the regression model. Outcomes will be summarized using medians and interquartile ranges for

continuous variables and numbers and percentages for categorical variables, by randomized group. Percentages will be reported to one decimal place. For the primary outcome and its sensitivity analyses, we will report adjusted odds ratios and adjusted risk differences derived from regression models. If a model fails to converge using the identity link function (for estimating the adjusted risk difference), only adjusted odds ratios will be reported. Methods for secondary analyses are detailed below; for secondary analyses aligned with the primary outcome analysis, we will report adjusted odds ratios. If the number of outcome events is insufficient to support reliable coefficient estimation (e.g., fewer than 10 events per parameter), no regression model will be fitted. We will consider the day of enrolment until the day of primary endpoint VL or until 28 months after enrolment if endpoint VL missing as study period for each participant.

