Effect modification (primary outcome): For effect modification of the primary outcome the following variables will be considered:

- i. Age groups (18-24, 25-39, 40-59, and ≥60 years)
- ii. Gender (female, male)
- iii. Cell phone access (yes, no)

Analyses will be performed as for the main primary outcome analysis including an interaction term between these potential effect modifiers and the randomized group. If an interaction term is found to be significant (p-value<0.05), effect estimates will be summarized descriptively by subgroup categories. As the study is not powered for these pre-planned subgroup analyses, no formal hypothesis testing will be done.

Secondary endpoints which may become the basis for additional claims: In case non-inferiority of the primary endpoint is established, these will be evaluated hierarchically.

- 4. Proportion of participants with viral re-suppression (<50 copies/mL) 24 months (16-28 months) after enrollment among all participants with an unsuppressed VL (≥ 50 copies/mL) during the first 12 months of follow-up: This analysis will include individuals with a VL ≥50 copies/mL in the first 12 study months and then directly follow the primary endpoint analysis.
- 5. Proportion of participants with sustained viral suppression (defined as >1 VL <50 copies/mL) during 24 months follow-up: This analysis will directly follow the primary endpoint analysis with endpoint adapted to sustained viral suppression <50 copies/mL throughout the study. Sustained viral suppression is defined as >1 VL <50 copies/mL from study start to end of 24-month window (0-28 months) along with no VL ≥50 copies/mL.

Secondary endpoints indicative of clinical benefit or harm: These will be evaluated independently of the primary objective and without hierarchy / multiplicity adjustment.

- 6. **Rate of mortality at 12 and 24 months after enrollment:** This analysis will use Cox regression adjusted for clinic and district by study arm.
- 7. **Proportion of participants with confirmed TB diagnosis at 12 and 24 months after enrollment:** This analysis will directly follow the primary endpoint analysis with endpoint TB diagnosis (window: 0 months to primary endpoint or 28 months).
- 8. **Disengagement from care at 12 and 24 months after enrollment:** This analysis will directly follow the primary endpoint analysis with endpoint disengagement from care at 24 months, defined as neither a documented visit attendance nor a VL measurement (window: 16-28 months).

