Secondary endpoints expressing supportive evidence:

- 9. Time to follow-up VL in case of an unsuppressed VL (≥ 50 copies/mL): This analysis will consider the time in weeks to follow-up VL in case of an unsuppressed VL (≥ 50 copies/mL) as outcome and use a multi-level linear regression model including clinic cluster as a random effect, arm allocation and the randomization stratification factor (district) as a fixed effect.
- 10. Time to ART regimen adaption in case of virologic failure: This analysis will consider the time in weeks to ART regimen adaption in case of virologic failure (defined as two consecutive VLs ≥1'000 copies/mL or three consecutive VLs ≥20 copies/mL from VITAL start 22.12.2022 and two consecutive VLs ≥50 copies/mL from 23.12.2022 − VITAL closure) as outcome and use a multi-level linear regression model including clinic cluster as a random effect, arm allocation and the randomization stratification factor (district) as a fixed effect.
- 11. Rate of clinic visits at 24 months after enrollment: This analysis will consider the number of clinic visits throughout the study period as outcome and use and use a multi-level Poisson regression model with offset study duration including clinic cluster as a random effect, arm allocation and the randomization stratification factor (district) as a fixed effect.
- 12. Proportion of participants with ART regimen modification due to virologic failure at 12 and 24 months among participants with virologic failure: This analysis will only include people with a virologic failure (defined as two consecutive VLs ≥1′000 copies/mL or three consecutive VLs ≥20 copies/mL from VITAL start 22.12.2022 and two consecutive VLs ≥50 copies/mL from 23.12.2022 VITAL closure). Then, this analysis will directly follow the primary endpoint analysis with endpoint ART modification.
- 13. **Proportion of participants having ever received TPT:** This analysis will directly follow the primary endpoint analysis with endpoint having ever received TPT by 24 months.

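### The study period never stops at death, transfer-out or withdrawal, so the visit-rate offset counts impossible person-time; the TB window follows each participant's viral load date (minor)

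*SAP*

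**What the plan says.** For every participant, the general paragraph of SAP section 6.2 takes "the day of enrolment until the day of primary endpoint VL or until 28 months after enrolment if endpoint VL missing as study period". By section 3.7 the endpoint VL is the one nearest month 24 within months 16 to 28, so the period lasts 16 to 28 months, and exactly 28 when no endpoint VL exists.

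Three secondary endpoints in section 6.2 depend on follow-up time:

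- **Endpoint 11, clinic visits:** "This analysis will consider the number of clinic visits throughout the study period as outcome", fitted with a "multi-level Poisson regression model with offset study duration".
- **Endpoint 7, confirmed TB:** the primary endpoint's logistic model, with "window: 0 months to primary endpoint or 28 months".
- **Endpoint 6, mortality:** "This analysis will use Cox regression adjusted for clinic and district by study arm". No end of follow-up or censoring event is given there.

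Section 5.4 lists the reasons for disengagement as "dead, hospitalized, transfer-out, stopped ART no information found after tracing" and adds study withdrawal, all reported by group. Section 4.3 sets the principle for the primary analysis: "we will analyse participant outcomes in the cluster they were enrolled in, independent of their follow-up".

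**The concern.** A rate needs a denominator during which the event could occur. A participant who dies at month 8 without an endpoint VL cannot attend the clinic afterwards, yet receives a longer exposure than a participant measured at month 24. Deaths, transfers and withdrawals therefore lower an arm's visit rate. Table 3 reads a lower visit rate as the favourable direction.

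For TB the fault is different. The logistic model has no term for observation time, and the window closes on the day of a VL. In a trial of VL-driven care, VL timing is something the intervention may change: endpoint 9 compares time to a follow-up VL. Equal TB hazards with different VL dates would give different proportions.

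For mortality, the SAP does not say whether the section 6.2 study period also ends the Cox follow-up. TB and mortality are two of the three safety endpoints in section 6.5.

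**Working it through.** **The plan's own figure.** Section 3.7 gives a participant enrolled on 10.10.2020 a window of 10.02.2022 to 10.02.2023. Adding 16 and 28 calendar months gives the same dates, so the range of 16 to 28 months is confirmed.

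**Inputs.** The SAP gives no exit, visit, VL-timing, TB or death rates, so all of these are assumed. I read the offset as the length of the section 6.2 study period.

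**(a) Visits.** Assume one visit every 3 months while in care in both arms. Stayers have their VL at month 24 (8 visits). A share d dies, transfers or withdraws at month m without an endpoint VL.

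- Visits per participant = (1 − d) × 8 + d × m/3
- SAP person-time = (1 − d) × 24 + d × 28
- Person-time ended at exit = (1 − d) × 24 + d × m

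With m = 8 the true rate is 1/3 = 0.3333 per month:

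| d | Visits | SAP months | SAP rate | SAP/true |
|---|---|---|---|---|
| 3% | 7.840 | 24.12 | 0.3250 | 0.975 |
| 5% | 7.733 | 24.20 | 0.3196 | 0.959 |
| 10% | 7.467 | 24.40 | 0.3060 | 0.918 |

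Rate ratios between arms with equal true rates:

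| Exits | m = 4 | m = 8 | m = 16 | Time ended at exit |
|---|---|---|---|---|
| 5% vs 3% | 0.980 | 0.983 | 0.990 | 1.00 |
| 10% vs 5% | 0.949 | 0.958 | 0.975 | 1.00 |

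Equal exits in both arms give 1.00 under either definition.

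**(b) TB.** Assume a hazard of 1% per year in both arms and everyone observed for T months, so that risk = 1 − exp(−0.01 × T/12).

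- T = 24: 1.980%
- T = 23: 1.898%, odds ratio against 24 months 0.958
- T = 22: 1.817%, odds ratio against 24 months 0.916

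The 2-month case is a difference of about 1.6 cases per 1,000. At the extremes, risk is 1.324% at 16 months and 2.306% at 28 months.

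A fixed 24-month proportion would not cure this, because early exits would count as TB-free. Take exits at month 8, where risk is 0.664%. An arm's proportion is then (1 − d) × 1.980% + d × 0.664%:

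- 5% vs 3% exits: 1.914% vs 1.941%, odds ratio 0.986
- 10% vs 5% exits: 1.849% vs 1.914%, odds ratio 0.965

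**(c) Mortality.** If the section 6.2 period did end Cox follow-up, deaths after an early endpoint VL and before month 24 would not count. Assume 85% have a VL at month V, and let r be the monthly hazard. The share of deaths by month 24 that is lost = 0.85 × mean of [exp(−rV) − exp(−24r)], taken as zero when V ≥ 24, divided by [1 − exp(−24r)]. At 1% per year this is about 1.75% with V uniform over months 22 to 26, and 3.5% over months 20 to 28.

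**The case against.** The strongest reply concerns weight. Section 4.1 intends no claims from the supportive endpoints and promises only descriptive statistics for them, and endpoint 11 is one. The SAP does not suggest that exits or VL timing will differ by arm. Choosing the VL nearest month 24 pulls the TB windows together. Section 6.2 also says that with "fewer than 10 events per parameter), no regression model will be fitted". If the model has 3 parameters, 30 events by month 24 at 1% per year need 30/(1 − exp(−0.02)) ≈ 1,515 participants, so a TB or mortality ratio may never be estimated. All of this stands and is why the point is minor. The event counts would still depend on the window.

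A second reply is that the section 4.3 principle could support visits per enrolled participant over the planned period, with people who transfer out kept in the denominator. That is a coherent quantity for transfers and deserves a sensitivity analysis. It does not rescue person-time after death.

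Three stronger readings are tempting but not supported:

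- A reader might infer that everyone who disengages is miscounted. Living people who stop ART or cannot be traced can still attend, and their absence of visits is real. People who leave after their endpoint VL are not affected either.
- A reader might infer a large visit bias. Exits of 20% against 10% at month 8 would give 0.91, but that is a stress case with no basis in the SAP.
- A reader might infer a biased mortality ratio. The SAP does not say that the study period cuts Cox follow-up, and the reference in section 6 to all follow-up up to the data freeze can be read as a data cut-off only. This is an ambiguity, not a contradiction. Shorter follow-up removes events and time together, so with equal hazards the ratio stays at about 1.00. Moving it requires an assumed excess death rate in people without a VL, which the SAP does not give.

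**Conclusion.** The concern holds as a minor one. For endpoint 11 the SAP fixes a rule that, followed as written, credits time in which no visit to the clinic was possible. The rate in an arm is understated by about 2.5% to 4% with 3% to 5% of exits at month 8. Any bias in the ratio requires exits to differ by arm. For endpoint 7, observation time depends on VL timing, and the odds ratio moves to about 0.96 or 0.92 only if one arm's VLs come 1 or 2 months earlier. For endpoint 6 a clarification is needed, and no bias is shown. Every size rests on assumed inputs. The primary endpoint and endpoints 4, 5 and 8 are not affected.

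**What to change.** - **Visits (endpoint 11):** end both the visit count and the offset at the earliest of death, transfer-out, withdrawal and the end of the study period. Keep living untraced participants at risk in the main analysis. Show transfer-outs kept at risk as a sensitivity analysis. Report each type of exit by arm.
- **TB (endpoint 7):** use one common horizon from enrolment for everyone, independent of the VL date. Analyse TB as a rate or time to event, with person-time ended at death, transfer-out or withdrawal. Do not replace the present window with a simple fixed-window proportion.
- **Mortality (endpoint 6):** state that follow-up runs to the same common horizon and is not cut at the endpoint VL, and list the censoring events.

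The cost is a few lines of SAP text and re-derived follow-up dates. It assumes that exit dates were recorded, since section 5.4 mentions only reasons. Section 1.4 shows that the SAP was already revised during analysis, so this change should be disclosed as made at that stage, with results under both definitions.

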1.4. SAP revisions

Version	Date	Justification for each SAP revision	Timing of SAP revision in relation to study
1.1	28.07.2025	- Change in secondary endpoint 13 due to data issues: updated from "having received a course of TPT throughout the study" to "having ever received a course of TPT," as the first TPT measurement was not consistently collected at enrolment, making the baseline estimate unreliable. - Change in sensitivity analysis 2 due to methodological clarification: updated from "multiple imputation" to "imputation," as a single imputation method was used rather than a multiple imputation approach - Change in secondary endpoint analyses: no longer reporting adjusted risk differences for secondary endpoints due to convergence issues. - Clarification: No regression model will be fitted if the number of events per model parameter is below 10, to avoid overfitting and to ensure reliable coefficient estimation.	During analysis

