3.1. Trial design

Full details of the trial are available in the published protocol (2).

VITAL is a multicenter, pragmatic, cluster-randomized, open-label, non-inferiority trial. The rationale for a cluster randomized design with clinics as clusters is to minimize the risk of cross-contamination between the study arms. Also, the pragmatic cluster-randomized design is the method of choice for the evaluation of the effect of a model of care on patient outcomes. The study is conducted at 18 clinics in two districts of Lesotho (Butha-Buthe, Mokhotlong).

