3.3. Sample size

We calculated the sample size for the non-inferiority cluster randomized design which corresponds to an individually randomized design multiplied by a design effect (3–5). We will use odds ratios (ORs) to assess the effect of the intervention on our binary primary endpoint. An OR of 1 corresponds to no relative effect, an OR >1 to a positive relative and an OR <1 to a negative relative effect in the intervention versus control clusters. We aim at testing the null hypothesis H_0 : OR \leq margin of non-inferiority (NI) versus the alternative hypothesis H_1 : OR > NI, where the rejection of the null hypothesis implies non-inferiority. The NI margin for the OR of reaching our primary endpoint is set to 0.8 (see section 3.4).

We estimated an intraclass correlation coefficient of 0.04 as the proportion of the variance explained by the cluster structure in our population and included the estimated mean cluster size and standard deviation to our design effect. Our desired type I error rate was chosen as 0.025. With 9 clusters in the intervention group and 9 clusters in the control group, we will have 85% power to detect a one-sided difference of >10% in the primary endpoint between the intervention and the control arm.

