3.4. Framework

This is a non-inferiority trial. If non-inferiority of the primary endpoint is established, we will assess superiority.

We chose a NI margin for the odds ratio of reaching our primary endpoint of 0.8, i.e., if the lower bound of the one-sided 97.5% confidence interval for the adjusted odds ratio for the primary outcome exceeds 0.8, then our intervention is non-inferior to standard of care. On an absolute scale, this non-inferiority margin corresponds to a higher absolute probability of failing to reach the primary endpoint of 5% in the intervention compared to the control group, if 65% of participants in the control arm will be engaged in care with documented viral suppression at 24 months follow-up.

If the lower bound of the two-sided 95% confidence interval for the adjusted odds ratio for the primary endpoint exceeds 1.0, we will consider our intervention superior.

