Primary outcome: For the analysis of the primary outcome, we will use a multi-level logistic regression model including clinic cluster as a random effect, arm allocation and the randomization stratification factor (district) as a fixed effect. Unavailability of a viral load or only an invalid viral load result in the predefined primary endpoint window (for any reason) will be considered as failure. Results will be reported as adjusted odds ratios and absolute differences with confidence intervals. For the primary endpoint, non-inferiority in the ITT population and superiority in ITT will be assessed but no statistical multiplicity adjustment will be needed because of the closed testing principle. For the non-inferiority comparison, a confidence interval approach will be used. Under the assumptions of the sample size calculation, non-inferiority is compatible with the lower bound of the one-sided 97.5% confidence interval for the adjusted odds ratio for the primary outcome exceeding 0.8. A figure illustrating the confidence interval and the non-inferiority margin will be presented. If the non-inferiority is established, then we will assess for superiority by assessing whether the two-sided 95% confidence interval of the adjusted odds ratio excludes 1.

Assessment of cost (primary outcome): We will analyse cost-effectiveness if the intervention is found to be superior or assess the budget impact if the intervention is found to be non-inferior. For the cost-effectiveness analysis, we will use the primary endpoint and mathematical models of HIV transmission. Costing data will include: (1) conversion rate of local currency to U.S. dollars at 6-month intervals over the life of the project; (2) costs of all commodities used in the intervention; (3) average time clients spent with intervention including transportation, (4) staff time and representative salaries; (5) local average wages of the target population; (6) remunerations to clinics; and (7) other relevant costs, including training of providers and transport costs.

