Time and motion studies are conducted to collect the costing data necessary to provide the intervention. All clinics contributed several time and motion observations. An experienced research assistant collects data on time required to complete each step of the intervention. Observing multiple visits allows estimation of the average time taken for each step. The time taken for research purposes (e.g. data collection) is noted separately from the estimated time needed for clinical services. In addition, interviews with study staff to quantify the effort required for each step of the intervention are conducted, as well as interviews with participants to assess opportunity costs. We also ask participants what expenses and opportunity costs they incurred while receiving the intervention. Furthermore, we collect data on the average cost of medical care in Lesotho associated with HIV infection and AIDS through literature review. A discount rate of 3% is used with sensitivity analysis of 0% to 5%.

Sensitivity analyses (primary outcome):

- Proportion of participants engaged in care (defined as documented visit attendance) with documented viral suppression (<1000 copies/mL) 24 months (16-28 months) after enrolment: The first sensitivity analysis assesses the robustness of the primary analysis to the primary endpoint definition by repeating the primary outcome analysis (ITT) with a VL cutoff modified to 1'000 copies/mL.
- 2. Proportion of participants engaged in care (defined as documented visit attendance) with documented viral suppression (<50 copies/mL) 24 months (16-28 months) after enrolment: The second sensitivity analysis assesses the robustness of the primary analysis to the primary endpoint definition by repeating the primary outcome analysis (ITT) with imputing the VLs of participants who were engaged in care but do not have a documented viral load at 24 months using the viral load history of the participants.
- 3. Proportion of participants engaged in care (defined as documented visit attendance) with documented viral suppression (<50 copies/mL) 24 months (16-28 months) after enrolment: The third sensitivity analysis assesses the robustness of the primary analysis to technical challenges with viral load result availability by repeating the primary outcome analysis in the per-protocol population defined as participants for whom all VL results were available in the VITALapp ≤31 days after phlebotomy during the study period.

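### The non-inferiority bound comes from a mixed logistic model on 18 clinics with no stated small-sample correction; with ordinary maximum-likelihood limits the one-sided error is about 3.5-5%, not 2.5%

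*SAP*

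**What the plan says.** SAP section 3.1 states: "The study is conducted at 18 clinics in two districts of Lesotho". Section 3.3 gives 9 clinics per arm and an intraclass correlation of 0.04, and says: "Our desired type I error rate was chosen as 0.025". Section 3.4 sets the decision rule. The intervention is non-inferior "if the lower bound of the one-sided 97.5% confidence interval for the adjusted odds ratio for the primary outcome exceeds 0.8", and superior if the two-sided 95% lower limit exceeds 1.0.

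For the analysis, section 6.2 says "we will use a multi-level logistic regression model including clinic cluster as a random effect, arm allocation and the randomization stratification factor (district") as fixed effects. On the limit itself it says only: "For the non-inferiority comparison, a confidence interval approach will be used". Section 6.6 names R but no package or estimator. Sections 4.1, 6.2, 6.3 and 6.6 state neither an interval type (Wald or profile likelihood) nor a degrees-of-freedom method or correction for the number of clinics.

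The same analysis is reused. The third sensitivity analysis proceeds "by repeating the primary outcome analysis in the per-protocol population". Secondary endpoint 4 takes participants with an unsuppressed viral load "in the first 12 study months and then directly follow the primary endpoint analysis", and endpoint 5 follows the same route. Endpoints 4 and 5 may support additional claims.

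**The concern.** Arm and district are constant within a clinic. However many participants are enrolled, the arm effect is judged against the variation among 18 clinics after three fixed coefficients are fitted (intercept, arm, district).

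Two things go wrong when such a model is fitted by ordinary ML and the limits use the normal or chi-square reference. The clinic variance is estimated too low, because ML makes no allowance for the three coefficients. The critical value is also too small, because it treats that variance as known. Both errors raise the lower limit.

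That limit is the trial's primary decision. If it is too high, non-inferiority is declared too often when the intervention is exactly at the margin. The superiority test and endpoints 4 and 5 inherit the fault. The closed-testing argument in section 4.1 assumes that each test in the sequence holds its own level.

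**Working it through.** **Inputs from the SAP.** 18 clinics, with arms split 5/5 in Butha-Buthe and 4/4 in Mokhotlong (Table 1); control proportion 65% and margin 0.8 (section 3.4); intraclass correlation 0.04 and one-sided level 0.025 (section 3.3).

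**Assumed.** The SAP does not give cluster sizes. Means of 50, 100 and 300 were used, with coefficient of variation (CV) 0 or 0.5.

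**The plan's own figures.**
- A one-sided limit at z = 1.960 gives exactly 0.025 if the clinic variance is known.
- Margin: odds 0.65/0.35 = 1.857; 1.857 × 0.8 = 1.486; 1.486/2.486 = 59.8%. The difference is 5.2 points, which agrees with the stated 5%.
- Power of 85% cannot be reproduced without the cluster sizes.

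**Clinic variance on the logit scale.** Reading 0.04 on the proportion scale: 0.04/(0.65 × 0.35) = 0.176. Reading it on the latent scale: (0.04/0.96) × π²/3 = 0.137.

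**Step 1: large-cluster limit.** With large clinics, each clinic's log-odds is effectively observed, and the problem becomes a linear regression with 18 observations and 3 coefficients. No cluster size or intraclass correlation is needed.
- Wald z with ML variance: the variance is RSS/18 instead of RSS/15, so the test rejects when t(15) > 1.960 × √(15/18) = 1.789. Tail: **4.7%**.
- Profile likelihood: 18 × ln(1 + t²/15) > 3.84, so t(15) > √(15 × (e^(3.84/18) - 1)) = 1.889. Tail: **3.9%**.
- Unbiased variance, still with z: t(15) > 1.960. Tail: **3.4%**.
- Unbiased variance with t(15): t(15) > 2.131. Tail: **2.5%**.

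**Step 2: simulation at true odds ratio 0.8.** The random-intercept logistic model was fitted by ML with adaptive Gauss-Hermite quadrature (15 nodes). The REML-type fit was restricted pseudo-likelihood (PQL). There were 8,000 runs per row; Monte Carlo SE is about 0.2 points. Entries are the percentage of false non-inferiority claims. Clinic variance is 0.176 except in the last row (0.137).

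| Mean size, CV | Wald z | Profile | ML SE, t(15) | REML-type, t(15) | Clinic log-odds, t(15) |
|---|---|---|---|---|---|
| 50, 0 | 4.6 | 3.9 | 3.5 | 2.6 | 2.5 |
| 50, 0.5 | 4.8 | 4.1 | 3.7 | 2.7 | 2.2 |
| 100, 0 | 4.4 | 3.7 | 3.4 | 2.6 | 2.6 |
| 100, 0.5 | 4.3 | 3.5 | 3.2 | 2.2 | 2.2 |
| 300, 0 | 4.5 | 3.7 | 3.5 | 2.5 | 2.5 |
| 300, 0.5 | 4.7 | 4.0 | 3.7 | 2.4 | 2.3 |
| 100, 0.5 (latent scale) | 4.9 | 4.0 | 3.5 | 2.4 | 2.4 |

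A separately written simulation (5,000 runs per setting, Monte Carlo SE about 0.3 points) gave Wald z 4.4-5.1%, profile 3.7-4.3% and clinic log-odds with t(15) 2.3-2.8%.

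**Step 3: cause.** With true variance 0.176, the mean estimate was 0.131-0.144 by ML and 0.174-0.176 by the restricted fit. At size 100, CV 0.5, the mean SE of the log odds ratio was 0.203 by ML and 0.221 by the restricted fit; the true SD was 0.225. Correcting only one part is not enough: ML SE with t(15) gives 3.2-3.7%, and restricted SE with z gives 3.1-3.6%.

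**Step 4: the other tests.**
- Superiority at odds ratio 1 (size 100, CV 0.5): upper-tail error 4.4% with Wald z, 3.6% with profile limits, 2.4% with REML-type t(15).
- A case like endpoint 4 (assumed 15 per clinic, 50% re-suppressed): 4.1%, 3.6% and 2.0%; clinic log-odds with a 0.5 correction, 2.3%. In 15.5% of these runs some clinic had no events or no non-events.

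**The case against.** The strongest reply is that the SAP does not prescribe Wald z or profile limits. A restricted fit with t limits would still be a multi-level logistic model of the kind described, so the provable defect is an unspecified interval and the inflated error is conditional on the analyst's choice. This stands as a description, and the conclusion is worded accordingly. It does not protect the plan. The interval is the decision rule, and fixing it is the SAP's task. The two common ML limits both fit the text and both miss 2.5%; only a correction that the text does not mention would hold it. The protocol might name one, but it was not available for this review.

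A second reply is that the inflation may depend on the intraclass correlation of 0.04. Further simulations (2,000-3,000 runs each, Monte Carlo SE 0.4-0.5 points) with clinic variance down to 0.022, or intraclass correlation down to 0.01, gave Wald z errors of 4.0-5.8%. The problem therefore persists at lower clinic variation. In these smaller runs and their companion settings, clinic-level t(15) gave 2.2-3.3%.

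Third, other corrections would serve, such as a permutation test or a bias-corrected variance with adjusted degrees of freedom. This is true; what matters is that one validated method is named.

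Last, version 1.1 is dated "During analysis" in section 1.4, so a new deciding bound would be a late change in an open-label trial. This also stands, and it is why the change needs an explicit post hoc label and both bounds must be shown.

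**Conclusion.** The concern holds. The SAP states a one-sided level of 0.025 but does not specify an interval that attains it with 18 clinics. Under ordinary ML, the false non-inferiority rate is about 3.5-4.3% with profile limits and 4.3-5.1% with Wald limits, or roughly 1.4 to 2 times the stated level (3.5/2.5 = 1.4; 5.1/2.5 = 2.04). The superiority test and endpoints 4 and 5 are affected in the same way.

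The figures assume normally distributed clinic effects, the Table 1 layout, a 65% control proportion and the assumed cluster sizes. The large-cluster limits of 4.7% and 3.9% need no cluster size and fall within the simulated ranges. Because the primary decision is affected and the remedy is short, this must be fixed before the result is interpreted.

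**What to change.** Keep the model and the odds ratio. In a dated SAP revision, labelled post hoc, specify for the primary endpoint, its sensitivity analyses and endpoints 4 and 5:

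1. A restricted (REML-type) clinic variance, naming the estimator (restricted pseudo-likelihood is the one checked here), with limits from t on (contributing clinics - 3) degrees of freedom. With all 18 clinics that is 15, critical value 2.131. Both parts are needed.
2. Or an unweighted regression of clinic log-odds on arm and district with the same t, adding 0.5 to events and non-events in every clinic if any clinic has none of either.

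Name one of these as the method, state that its bound decides, and report the uncorrected bound beside it.

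**Cost.** A few lines of text and R code, and no new data. At size 100, CV 0.5, the SE rises by 0.221/0.203 = 1.089 and the critical value by 2.131/1.960 = 1.087. The interval is therefore 1.089 × 1.087 = 1.184 times as wide as with Wald limits, about 18% wider; the increase over profile limits would be smaller. An effect with 85% power at z = 1.960 has 80.0% by noncentral t(15). Simulation at an assumed size of 300 (CV 0.5, 4,000 runs) gave 82.7% for the restricted fit and 81.7% for the clinic-level method. These power figures are indicative only, because the SAP's 85% cannot be reproduced without its cluster sizes.
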